5.6.2.3. Phase allocation of Adverse Events

Solicited events are always allocated to the respective Post Dose period.

Step 1: Allocation of events to the periods:

Adverse events in the SDTM database are allocated to periods based on their start date/time. If the start date/time of an event falls between (or on) the start and stop date/time of a period, the AE is attributed to that period (treatment-emergent principle).

- In case of partial start or stop dates (i.e. time and/or day and/or month and/or year missing), the events are allocated to the periods using the available partial information on start and end date; no imputation will be done. If, for instance, the AE start date only month and year are available, these data are compared to the month and year information of the periods. This rule may lead to multiplication of the event as a consequence of its assignment to multiple periods.
- In case of a completely missing end date, the date is imputed by the cut-off date of the analysis for participants still ongoing in the study, and by the end date of the last period for participants who discontinued or completed the trial. In case of a completely missing start date, the event is allocated to the first active treatment phase (post dose 1 period), except if the end date of the AE falls before the start of the first active treatment phase (post dose 1 period).

Step 2: Combination of events:

Overlapping/consecutive events are defined as events of the same participant with the same preferred term which have at least 1 day overlap or for which the start date of an event is 1 day after the end date of the preceding event. Overlapping/consecutive events may be combined into one AE or not, according to the following rules:

- 1) If overlapping/consecutive events start in one of the following periods - Screening or post dose extension (i.e. non-active periods) - followed by an AE in - post-dose period (active period) - they are allocated to their respective periods and are considered as separate events.
- 2) In case overlapping/consecutive events start within a single period, they are considered as one and the same AE. The individual events which contribute to this AE are retained as individual records in the ADaM database but are assigned the same onset, period, and total duration. All related attributes to the AE/phase/period should also be consistent with the new event.
- 3) In case overlapping/consecutive events start in both an active period followed by a non active period, they are allocated to the active period only and are considered as one and the same AE. The individual events which contribute to this AE are retained as individual records in the ADaM database but are assigned the same onset, treatment period, and total duration. All related attributes to the AE/phase/period should also be consistent with the new event.
- 4) In case an active period is followed by another active period, and the overlapping/consecutive events start in both periods, they are allocated to their respective period and are considered as separate AEs. The same rule applies for 2 non-active periods.

Remarks:

1. Events can only be combined into one and the same AE if their start and stop dates are known.
2. In case the completely missing end date is imputed (for period allocation), this date is also considered as a complete date.
3. Time is not considered when determining overlap of events.

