5.6.2.4. Missing Data

Missing AE data will not be imputed. Participants who do not report an AE will be considered as participants without an adverse event. An AE with missing severity or relationship will be considered as the reported AE, but will be considered as not reported for the severity or relationship. For example, an AE with missing severity will be considered as an AE reported for the analysis of any grade, but will be considered as not reported for the analysis of at least grade 3.

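### An AE that resolved without a recorded stop date is treated as lasting to the end of observation, so a later SAE with the same preferred term can be re-dated into the 28-day post-booster period

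*SAP*

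**What the plan says.** All of the rules are in SAP section 5.6.2.3.

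- **Imputation (Step 1).** "In case of a completely missing end date, the date is imputed by the cut-off date of the analysis for participants still ongoing". Anyone who has left or finished the study gets the close of their final period instead. Events are placed in periods by their start date and time.
- **Candidates for combination (Step 2).** These include "events of the same participant with the same preferred term which have at least 1 day overlap". An event starting the day after the previous one ends also qualifies.
- **Rule 3.** If the first event starts in an active period and the next in a non-active one, "they are allocated to the active period only and are considered as one and the same AE". The records stay in ADaM but share one onset, one period and one total duration. No exception is made for seriousness.
- **Remark 1.** "Events can only be combined into one and the same AE if their start and stop dates are known".
- **Remark 2.** "In case the completely missing end date is imputed (for period allocation), this date is also considered as a complete date".

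Section 5.6.2.4 opens with a general statement: "Missing AE data will not be imputed". Section 5.1.2 (Table 1) ends Post-dose 1 at 28 days after vaccination and starts Follow-up 1 after that. Section 5.6.2.2 plans TTS tables for the entire study, Post-dose 1 and Follow-up 1, and says that SAE tables are built the same way.

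**The concern.** When an event has a full start date, its imputed end date plays no part in period allocation. Its effect comes through Remark 2, when overlap is judged. A blank end date can mean that the event was still going on, or that it ended and nobody wrote down when. The SAP handles both in the same way, as if the event lasted to the end of observation.

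For the second kind that is false. A new and serious event months later, coded to the same preferred term, would be reported as part of something that began within 28 days of the booster. The split between Post-dose 1 and Follow-up 1 is what a reader uses to judge closeness to vaccination. SAEs are few, so a single re-dated case can be visible in one dose group.

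**Working it through.** The SAP gives no figure to reproduce, so the check applies the written rules to illustrative pairs of events.

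**Inputs from the SAP:** Post-dose 1 ends 28 days after vaccination (Table 1); allocation is by start date (Step 1); imputation, overlap, rules 2 to 4 and the Remarks are as in 5.6.2.3.

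**Assumptions for the illustration:** vaccination is day 0, so Post-dose 1 is days 0 to 28. Follow-up 1 starts on day 29 and is non-active. The participant's last date is day 180. The later event is an SAE on days 120 to 130. Both events are unsolicited and have the same preferred term; the first is not serious.

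**Overlap test:** with first event (s1, e1) and later start s2, the two are overlapping or consecutive if s2 ≤ e1 + 1.

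| First event | e1 used | Test | Result for the SAE |
|---|---|---|---|
| Day 3, end blank, Remark 2 applied | 180 | 120 ≤ 181, true | Rule 3: Post-dose 1, onset day 3 |
| Day 3, end recorded as day 8 | 8 | 120 ≤ 9, false | Follow-up 1, onset day 120 |
| Day 3, end blank, Remark 1 alone | none | not combined | Follow-up 1, onset day 120 |
| Day 40, end blank, Remark 2 applied | 180 | 120 ≤ 181, true | Rule 2: Follow-up 1, onset day 40 |
| Day −5 (Screening), end blank, Remark 2 applied | 180 | 120 ≤ 181, true | Rule 4: separate, Follow-up 1, onset day 120 |

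In the first row the SAE's onset moves 120 − 3 = 117 days earlier. The combined event runs from day 3 to day 180, a span of 180 − 3 = 177 days, against 130 − 120 = 10 days for the SAE as recorded. Two distinct events become one. If the participant has no other SAE, the SAE table gains one participant in Post-dose 1 and loses one in Follow-up 1. The entire-study count is unchanged.

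The choice of day 180 does not matter. With e1 set to the last date L, every later event in the data has s2 ≤ L, so the test is always met. Any Follow-up 1 event with the same preferred term is absorbed.

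The fourth and fifth rows limit the point: a move into the 28-day period needs a first event that starts in Post-dose 1.

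**The case against.** The best defence is that the trigger is narrow and little is lost.

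- Partial stop dates are not imputed, so Remark 1 still blocks combination for them. Only a completely blank end date qualifies. If the blank means the event is ongoing, merging is reasonable. Nothing in the SAP shows that resolved events are left without any stop date.
- No record disappears. Individual records stay in ADaM, listings or narratives are planned for SAEs and AESIs, and the tables are descriptive. The shift is towards the vaccination window, which is the cautious direction.
- Rule 1 gives Screening and a post-dose extension as the non-active periods. Table 1 has no post-dose extension, so taking Follow-up 1 as non-active is an inference, though the only workable one.

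All of this stands, and it makes the point small. It does not make the period split right for an event that had resolved.

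A reader might also infer more than the text supports:

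- *That Remark 2 contradicts Remark 1.* It follows directly and states when an imputed date counts as complete. It qualifies Remark 1. The tension with 5.6.2.4 is also slight: after its opening sentence that section deals with unreported AEs, severity and relationship, and 5.6.2.3 is the specific rule for dates.
- *That allocation depends on the cut-off used for imputation.* Any later event in the data overlaps whichever end date is filled in. For completed or discontinued participants the imputed date is the end of the last period anyway.
- *That thrombotic AESI counts in the 28 days are inflated.* Combination needs the same preferred term, and the SMQ-search AESI table is built on preferred terms. An earlier event with that term in Post-dose 1 is already counted there.
- *That an early solicited headache shows the problem.* Solicited events are taken from separate CRF pages, have their own allocation rule and are tabulated apart. The point concerns unsolicited AEs.

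**Conclusion.** The point holds in a limited form. Under 5.6.2.3, an unsolicited AE that began in Post-dose 1 and resolved without any recorded stop date absorbs every later event with the same preferred term. A later SAE then takes the first onset and moves from Follow-up 1 to Post-dose 1. The Post-dose 1 versus Follow-up 1 split, the onset, the duration and the number of distinct events are distorted. Entire-study participant counts, listings and narratives are not, and no hypothesis test is involved.

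This rests on reading Follow-up 1 as the non-active period and on some blank end dates belonging to resolved events. The SAP gives nothing from which the number of such events could be derived, so the overall size is unknown. Each affected pair of the kind worked through above shifts one SAE between periods. Severity is low; the reason to act is that the change is cheap.

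**What to change.** Replace Remark 2 in 5.6.2.3 with:

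> *An imputed end date is used to combine events only if the AE is recorded as ongoing / not recovered; otherwise events with a completely missing end date are not combined and each keeps its own onset and period.*

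Add to 5.6.2.4 that AE end dates are the exception to the rule of no imputation.

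The cost is SAP wording and one condition in the AE derivation, assuming that the outcome of each AE is recorded. Ongoing events are still merged as now. The downside is that a few single illnesses entered as two records, with no stop date on the first, may be counted as two events.

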5.6.2.4. Missing Data

Missing AE data will not be imputed. Participants who do not report an AE will be considered as participants without an adverse event. An AE with missing severity or relationship will be considered as the reported AE, but will be considered as not reported for the severity or relationship. For example, an AE with missing severity will be considered as an AE reported for the analysis of any grade, but will be considered as not reported for the analysis of at least grade 3.

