4. POPULATIONS (ANALYSIS SETS) FOR ANALYSIS

For vaccine studies, study intervention assignment will follow the *as treated principle* i.e., all analyses will be presented by the vaccine actually received.

Population	Description
All screened participants (ALL)	The “all screened participants” set includes all participants who were screened, regardless of whether they were enrolled and/or randomized.
All randomized participants (ALL RANDOMIZED)	The “all randomized participants” set includes all participants who were randomized to one of the treatment groups.
Full Analyses Set (FAS)	The full analysis set includes all participants with documented study vaccine (Ad26.COV2.S) administration.
Per Protocol Immunogenicity Set (PPI)	The per protocol immunogenicity analysis set includes all vaccinated participants for whom post-baseline immunogenicity data are available and excludes participants with major protocol deviations expected to impact immunogenicity outcomes. In addition, samples obtained after natural SARS-CoV-2 infection will be excluded from this analysis set.
Non-Inferiority Analysis Set (NI)	The non-inferiority analysis set includes all PPI participants who are SARS-CoV-2 seronegative at baseline.

Pfizer BNT162b2 external samples	The Pfizer BNT162b2 external samples analysis set includes individuals, selected from biobanks or clinical studies, who received 2 doses of Pfizer BNT162b2 vaccine as primary vaccination and for whom blood samples are available between 2 weeks and 2 months post primary vaccination series with Pfizer BNT162b2 vaccine.
----------------------------------	--

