5.4. Secondary Endpoint(s) Analysis

The secondary endpoints include:

- To assess the safety and reactogenicity of Ad26.CO2.S as booster vaccinations in adults.
 - Solicited local and systemic adverse events (AEs) for 7 days after booster vaccination.
 - Unsolicited AEs for 28 days after booster vaccination.
 - Serious adverse events (SAEs) and adverse events of special interest (AESIs) throughout the study (from booster vaccination until end of the study).

- To assess the neutralizing and binding antibody response to the original strain, leading variant of high consequence or concern* and other relevant variants of concern, induced by booster vaccination in adults who have previously completed single-dose primary vaccination with Ad26.COV2.S at the 5×10^{10} vp dose level.
 - Serological response to vaccination and antibody titers, as measured by VNA, against the original strain, leading variant of high consequence or concern* AND other relevant variants of concern, 14 days and 28 days after Ad26.COV2.S booster vaccination.
 - Antibodies binding to SARS-CoV-2 relevant variants of concern or individual SARS-CoV-2 proteins (eg, S and/or receptor-binding domain [RBD] proteins from the SARS-CoV-2 variants of concern) by ELISA and/or MSD.
 - Antibodies binding to the SARS-CoV-2 nucleocapsid (N) protein at Day 1 (N-serology).
- To assess the neutralizing and binding antibody response to the original strain, leading variant of high consequence or concern* and other relevant variants of concern, induced by booster vaccination in adults who have previously completed primary vaccination with Pfizer BNT162b
 - Same endpoints as above

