5.6. Safety Analyses

All safety analyses will be based on the FAS based on actual intervention received, unless otherwise specified.

All continuous safety variables, descriptive statistics by intervention group will include the N, mean, standard deviation, median, minimum, and maximum. Categorical variables will be summarized by vaccination group using frequency counts and percentages. All safety data summary will be presented by Cohort where Cohort 1 includes participants who received Ad26.COV2.S as primary vaccination; and Cohort 2 includes those who received BNT162b2 as primary vaccination, unless specified otherwise. In addition, selected safety results will be presented in the same output with both cohorts.

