5.6.2. Adverse Events

5.6.2.1. Definitions

Solicited AEs shown in the tables are extracted from the investigator assessment pages (CE) of the CRF. For unsolicited AEs, only the AEs within the 28-day period following vaccination will be presented in the safety tables except for SAEs and AEs of Special Interest (AESI) which will be captured and tabulated in the outputs covering the whole study period. All other collected unsolicited adverse events will be presented through listings.

By definition, solicited administration site symptoms are considered to be related to the study vaccine.

The severity of AEs will be classified as grade 1 to 4. Solicited events that are graded less than grade 1 are not considered AEs. If grade is not present, grading is assigned based on the grading list in Appendix 11.

Respiratory tract infections due to SARS-CoV-2 infection will be tabulated and listed separately. Respiratory tract infections not due to SARS-CoV-2 infection will be reported as AEs by System Organ Class and Preferred Term if they occur between the time of vaccination through the following 28 days. Respiratory tract infections recorded as AEs in the eCRF will be excluded from AE analysis if the molecular test result for that event is positive for SARS-CoV-2. In general, any (S)AEs caused by molecularly confirmed SARS-CoV-2 infection will be removed at the analysis level from the (S)AE listings and tables and presented separately.

This study defines thrombosis with thrombocytopenia syndrome (TTS) as an AE of Special Interest (AESI), cf. protocol sections 8.3.1 and 8.3.7.1. Suspected AESIs will be adjudicated by a committee to determine whether they fulfill the definition(s) for TTS (and consequently, whether they are confirmed AESIs).

If additional information (e.g. adjudicated cases, associated lab tests) becomes available in the clinical database, additional statistical analyses may be specified in the DPS.

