5.6.2.2. Analysis of Adverse Events

Number and percentage of participants with at least one particular AE (unsolicited/solicited) will be tabulated. Solicited AEs will be summarized by class (administration site/systemic) and Preferred Term. Unsolicited AEs will be summarized by System Organ Class and Preferred Term.

For solicited AEs, the following tables will be provided: summary; by worst severity grade; at least grade 3; related (systemic only); time to onset (in days); and duration (in days) for most frequent events and body temperature. Note: Duration is defined as number of days from the start of the event until resolution of the event. The time to first onset is defined as (date of first onset – reference date + 1). The reference date is the start date of the vaccination period.

For unsolicited AEs, the following tables will be provided: summary table (including SAE, fatal outcome, and discontinuation); all events; most frequent; at least grade 3; permanent stop of vaccine; related; and SAE.

Tables will be provided to summarize the occurrence of TTS. These tables will cover the entire study period, post-dose 1 (booster) and follow-up 1 (similar to SAE tables). The following summary tables will be provided on suspected and probable suspected AE of Special Interest (AESI) by vaccine group:

1. Number of Suspected AEs of Special Interest (AESI) (as reported by Investigator) by SMQ and Preferred Term
Note: Suspected AESI as reported by investigator and presented by: Embolic and thrombotic events (SMQ); Haematopoietic thrombocytopenias (SMQ) (broad) or HLT Thrombocytopenias; Other SMQ.
2. Number of Suspected AEs of Special Interest (AESI) (identified through SMQ search) by SMQ and Preferred Term
Note: Suspected AESI: Embolic and thrombotic events (SMQ), Haematopoietic thrombocytopenias (SMQ) (broad) or HLT Thrombocytopenias
3. Number of Probable AEs of Special Interest (AESI) qualified for assessment by SMQ and Preferred Term
Note1: Probable AESI qualified for assessment: [Embolic and thrombotic events (SMQ)] and [Haematopoietic thrombocytopenias (SMQ) (broad) or HLT Thrombocytopenias or platelet count below normal ranges per local or central laboratory report or platelet count < 150 × 10E9/L]

Platelet counts will be prospectively collected for AESIs (in LB domain). These will be used to identify participants who will be reported in 3 above and will be presented in participant narratives.

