5.6.3.2. Vital Signs and Physical Examination Findings

Physical examination findings will be summarized at baseline. A listing of the abnormalities will be made.

Vital signs including body temperature, pulse/heart rate, respiratory rate, and blood pressure (systolic and diastolic) will be summarized over time, using descriptive statistics. Abnormalities emerging after vaccination will be tabulated by worst abnormality grade using the FDA table in appendix 10.

A listing of participants with pyrexia/fever according to the FDA grading table will be provided. In addition, temperature measurements (whether obtained from the diary or from on-site assessments) will be allocated to predefined temperature intervals (from 37.5° C to 40°C, in half degree increments, e.g., <37.5; 37.5 to <38; 38 to <38.5; ... >40, and tabulated.

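### Main SAP 5.6.2.4 counts a vaccinated participant with no solicited assessment as free of solicited reactions, which can only lower reactogenicity percentages, by an unknown and possibly small amount

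*SAP*

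**What the plan says.** All references are to the main SAP unless stated otherwise.

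- Section 5.6 sets the denominator: "All safety analyses will be based on the FAS based on actual intervention received, unless otherwise specified".
- Section 4 defines that set: "The full analysis set includes all participants with documented study vaccine (Ad26.COV2.S) administration". No safety data after the dose are required.
- Section 5.6.2.2 treats both kinds of event together: "Number and percentage of participants with at least one particular AE (unsolicited/solicited) will be tabulated".
- Section 5.6.2.4 opens with "Missing AE data will not be imputed" and continues with "Participants who do not report an AE will be considered as participants without an adverse event".
- Section 5.6.2.1 names the source of the solicited data: "Solicited AEs shown in the tables are extracted from the investigator assessment pages (CE) of the CRF". It also says that a solicited reaction below grade 1 does not count as an AE.
- Section 5.4 lists this secondary endpoint: "Solicited local and systemic adverse events (AEs) for 7 days after booster vaccination".

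No section sets another denominator for solicited events. The disposition list in 5.2 has no count of participants with solicited data, and no completion table or sensitivity analysis is planned for them.

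**The concern.** For unsolicited events, treating no report as no event is the usual convention and is not in question. Solicited events are different because every participant is to be asked about the same reactions over a fixed 7 days. Having been assessed without a reaction and not having been assessed are then two separate facts. The rule in 5.6.2.4 merges them. Although that section says nothing is imputed, it in effect imputes the absence of a reaction.

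The planned tables could not reveal this. Neither a participant with no reaction nor one who was never assessed contributes an AE, and the number in the second group is not shown.

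The percentages are the result for a secondary endpoint, and the error has a direction: it can only make the booster look better tolerated. The plan does require data elsewhere. The per-protocol immunogenicity set needs post-baseline data, and the sequencing denominator in supplemental SAP 5.4.3 is limited to participants with sequencing data.

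**Working it through.** The SAP states no reactogenicity rate and no share of missing assessments, so it has no figure to reproduce. The rates below are assumptions, shown as ranges.

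**Notation**
- m = share of the FAS with no solicited assessment
- p = reaction rate among those assessed
- q = reaction rate among those not assessed

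**Formulas**
- True FAS rate = (1 − m)p + mq
- Rate reported under 5.6.2.4 = (1 − m)p
- Error of the plan's rule = (1 − m)p − [(1 − m)p + mq] = −mq
- Error if only assessed participants form the denominator = p − [(1 − m)p + mq] = m(p − q)

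The plan's error is never positive. It is zero if nobody is missing or if none of the missing reacted.

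**Step 1. Those without data react like the rest (q = p).** The reported rate is then true rate × (1 − m), and the understatement is p × m, in percentage points:

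| Assumed p | m = 2% | m = 5% | m = 10% | m = 20% |
|---|---|---|---|---|
| 20% | 0.4 | 1.0 | 2.0 | 4.0 |
| 60% | 1.2 | 3.0 | 6.0 | 12.0 |
| 80% | 1.6 | 4.0 | 8.0 | 16.0 |

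**Step 2. Those without data react differently.** With p = 60% and m = 10%:

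| q | True FAS rate | Plan reports | Error (points) | Assessed only | Error (points) |
|---|---|---|---|---|---|
| 0% | 54% | 54% | 0 | 60% | +6 |
| 30% | 57% | 54% | −3 | 60% | +3 |
| 60% | 60% | 54% | −6 | 60% | 0 |
| 90% | 63% | 54% | −9 | 60% | −3 |

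The two errors are equal in size when q = p/2. Below that the plan's rule is closer to the truth; above it the assessed-only denominator is closer.

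**Step 3. Dose groups.** Take two groups with the same reaction rate of 60% (q = p).
- Equal m: both are lowered equally, and no false difference arises.
- m of 5% and 10%: 57% and 54%, a false difference of 3 points.
- m of 5% and 15%: 57% and 51%, a false difference of 6 points (ratio 51/57 = 0.895).

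**The case against.** Several points on the other side are sound.

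- A reader might infer that solicited rates fall in proportion to missing diaries. The SAP does not support that. The tables draw on the investigator's CE pages, and 5.6.3.2 mentions a diary only for temperature. A lost diary matters only if it leaves the CE page empty. Proportionality also needs q = p.
- A reader might infer that the rule will create or hide a dose gradient. Nothing in the SAP shows that completion differs between groups. Under 5.8.2, participants and sites stay blinded to study end, which makes this less likely. The safety summaries are descriptive with no planned test between doses, and the objective in 5.4 concerns the booster in adults rather than a dose comparison.
- Changing the denominator does not remove all bias. As step 2 shows, it swaps one assumption about the missing participants for another, and the SAP cannot settle which is closer.
- Section 5.6 allows exceptions, and section 1 says that Data Presentation Specifications could add detail.

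These points limit the size and certainty of the bias. They leave the rule as it is: 5.6.2.4 is unqualified, the SAP sets no exception for solicited events, and followed as written it classes unassessed participants as non-reactors without showing how many there are.

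**Conclusion.** The point holds as a defect in a stated rule. Solicited-event percentages over the FAS are biased downward by m × q and never upward. With an assumed 60% rate and q = p, the understatement is 1.2 points at 2% unassessed and 6.0 points at 10%. The true m is not in the SAP and may be small, in which case little changes. With equal reaction rates, groups would differ spuriously only if m differs between them, and the SAP gives no evidence that it does. The conclusion rests on reading sections 4, 5.6, 5.6.2.2 and 5.6.2.4 together, and on no unseen specification setting another denominator.

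**What to change.** - In 5.6.2.4, limit the rule that no report means no event to unsolicited AEs, SAEs and AESIs.
- For solicited AEs, use as denominator the FAS participants with at least one solicited assessment recorded in the 7 days after vaccination. The SAP does not say how the CE pages record a participant who was asked and had no reaction, so the flag must be defined to count that participant as assessed.
- Tabulate, by dose group and cohort, the number of FAS participants with no solicited assessment.
- State that this denominator assumes solicited data are missing at random.
- Keep the full-FAS percentage as a supplementary lower bound. It is one because q cannot be below zero.

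The cost is a short change to the SAP text, one denominator flag and one added count. Stated reactogenicity rates become slightly higher, by a factor of 1/(1 − m); in the 60% example with 2% missing, 58.8% becomes 60%. If hardly anyone is missing, the results barely move and the new count shows it.
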